7.3. STUDY ENTRY

Randomisation will be performed by using Interactive Voice Response System (IVRS) or Interactive Web Response System (IWRS).

Once written consent has been given by the patient, all inclusion/exclusion criteria must be checked by the investigator in order to confirm eligibility, prior to IVRS (or IWRS) randomisation procedure. The following information will be required when the investigator calls the IVRS or logs in IWRS for patient enrolment:

- study code,
- personal user access number and secret code
- institution name, investigator's name and country
- patient's birth date (day/month/year)
- answers to the questions relating to the stratification factors
- patient's eligibility.

The IVRS / IWRS will randomly assign the patient to one of the two treatment arms and will allocate the patient a registration number that will be communicated to the investigator. In parallel, the sponsor will receive this registration number as well as any information submitted by the investigator during the randomisation procedure.

The patient number will have six digits. The first two digits identify the country; the third and fourth, the centre; and the last two digits the patient within the centre. This patient registration number must be reported on all CRF pages and in any study document. A patient who has not been randomised and registered before the first administration will not be accepted for the study at a later date.

Randomisation is the starting point of the study, it is mandatory not to exceed an interval of 1 week between the date of registration and the start of the study treatment. In any case, all events occurring after registration must be recorded in the CRF /eCRF and will be taken into account in the analysis, whether the patient received the study treatment or not.

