7.4. EVALUATION DURING THE STUDY PERIOD

The treatment period begins on the day of randomisation and continues until 30 days after the last study treatment administration.

The following assessments need to be completed throughout the treatment period:

Table 19: Assessments during the treatment period

Assessments	Timing - Comments
PHYSICAL EXAMINATION including weight, blood pressure and pulse, temperature, performance status (WHO score)	To be performed at day 1 of each cycle.
REVIEW OF SYMPTOMS, TOXICITY AND TREATMENTS	To be performed at day 1 of each cycle. All clinical findings and results from any complementary examination should be recorded in the CRF / eCRF.
LABORATORY TESTS (1)	
Haematology	- To be performed within 24 hours on days 1 and 8 of each cycle in arm A and before each weekly administration in arm B - In case of fever or infection according to institutional standards and investigator decision.
Serum chemistry	- To be performed within 24 hours before day 1 of each cycle in both arms (except glucose, total protein and albumin every 6 weeks)
ECG	- To be performed on D1 of the first cycle before and after drug administration in both arms and then every two cycles in both arms
TUMOUR ASSESSMENT (2)	To be performed every 6 weeks (+/- 3 working days) from randomisation (regardless of the timing of treatment cycles). All sites identified at baseline must be evaluated at each tumour assessment.
Health-related QUALITY OF LIFE (EORTC QLQ-C30 and QLQ H & N 35)	To be assessed every 6 weeks

(1) Haematology: complete blood cell count.

Serum chemistry: transaminases, alkaline phosphatase, total bilirubin, total protein, albumin, urea, creatinine and calculated (Cockcroft-Gault) creatinine clearance, glucose, calcium, sodium, potassium, magnesium, chloride, bicarbonate

(2) Tumour assessment: all target lesions (measurable disease) and non-target lesions (non-measurable disease) found at baseline should be re-investigated at each tumour assessment. Additional examinations may be performed if appearance of new lesions is suspected.

- Only the lesions found at baseline must be re-investigated. The same methods of assessment used at baseline should be used throughout the study to ensure comparability (*i.e.* scans performed immediately following bolus contrast administration using a standard volume of contrast, the identical contrast agent and preferably the same scanner).

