- A patient who wishes to stop the study treatment may do so at any time but must inform the investigator. In this case, the investigator should attempt to contact the patient as soon as possible for a final assessment in order to: i) evaluate the patient's clinical condition, ii) if necessary, take the appropriate therapeutic measures: management of an adverse effect or concomitant disease, prescription of another treatment.
- A patient who wishes to withdraw his/her consent from the study participation for any reason may do so at any time but must inform the investigator. In this case, the investigator should attempt to contact the patient as soon as possible for a final assessment in order to: i) have the patient's decision written in the consent form, ii) obtain the reason for withdrawal and report it in the CRF / eCRF, iii) evaluate the patient's clinical condition, iiiii) if necessary, take the appropriate therapeutic measures: management of an adverse effect or concomitant disease, prescription of another treatment.
- Any other reason to be documented.

All patients who have received at least one dose of study drug will be evaluable for safety analysis. In all cases, available data will be retained for the safety analysis.

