### **5. SAFETY PARAMETERS**

#### **5.1. ADVERSE EVENTS**

Each patient will be assessed for occurrence of adverse events. The CTCAE version 3.0 (publish date 9 Aug 2006) will be used. Adverse events not classified by the CTCAE will also be reported and graded according to their severity: mild (grade 1), moderate (grade 2), severe (grade 3), life-threatening or disabling (grade 4), sudden death (grade 5), not applicable in case of progression or adverse event not gradable according to CTCAE and leading to dose modification (NA).

Treatment Emergent Adverse Events (TEAE) will be considered for analysis of adverse events. A TEAE is defined as any event that first occurred during the treatment period (i.e. from first drug administration date up to last administration date + 30 days) or that “worsened” during that study period. The definition of “worsening” is described below:

- Any increase in the grade (according to CTCAE) compared to baseline sign or symptom, or
- Any sign or symptom becoming serious during the study period, or
- Any sign or symptom requiring a modification of the study drug administration, or
- Any sign or symptom becoming possibly, probably or definitely related to the study drug

An adverse event that meets one of the criteria described above will be considered as TEAE and reported in the analyses for the remainder of the study, even if the TEAE downgrades to baseline situation.

Baseline situation of the pre-treatment adverse events will be determined by using:

- the worst grade of the adverse events during the pre-study period (within 2 weeks prior to treatment),
- the seriousness of the event during the pre-study period,

This situation will be used as comparator to determine whether an existing adverse event during study period becomes treatment-emergent.

The adverse events will be classified using the Medical Dictionary for Regulatory Activities (MedDRA). The implementation of this international terminology in the Oracle Clinical® database will be performed using the available version of MedDRA (Version 19.0). Each description of the toxicity (verbatim) will be associated with the five following items:

- System Organ Class (SOC),
- High Level Group Term (HLGT),
- High Level Term (HLT),
- Preferred Term (PT),
- Lowest Level Term (LLT).

Two sets of events will be considered:

- all adverse events regardless of relationship to treatment,
- the adverse events that are possibly, probably or definitely related to treatment,

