*Of note, if the causality is missing, the AE will be considered as related to study treatment*

A patient will be evaluable for non-haematological toxicity if at least one drop of any treatment was given and the toxicity has been assessed by the investigator. The patient will be analysed in the treatment arm he/she was effectively treated.

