### **7.4. EVALUABLE POPULATION FOR SAFETY**

All randomised and treated patients will be included in the safety analysis. They will be analysed in the treatment arm they actually received.

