### 11.1. OVERVIEW OF THE SAFETY

The adverse events incidence, overall and per CTCAE grade, will be presented. The worst CTCAE grades or maximum severity grades (for non haematological adverse events not classified by the CTCAE) will be analysed by patient, and by treatment arm, regardless or not to the relationship to treatment.

For definition of evaluable patient for non-haematological and evaluable cycle/patient for haematological and biochemical toxicity, see § 5.1, § 5.3 and §5.4, respectively.

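### The SAP gives two denominators for non-haematological adverse events: all treated patients, or only treated patients whose toxicity was assessed

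*SAP*

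**What the plan says.** **Who is counted.** Protocol 7.6 is unconditional: "All patients who have received at least one dose of study drug will be evaluable for safety analysis". It adds that available data are always kept for that analysis. Protocol 11.3.4 likewise takes all treated patients. SAP 7.4 agrees: "All randomised and treated patients will be included in the safety analysis". The opening of SAP section 11 names the 7.4 population for the safety analysis.

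SAP 5.1 sets a narrower rule. A patient is evaluable for non-haematological toxicity "if at least one drop of any treatment was given and the toxicity has been assessed by the investigator". SAP 11.1 makes this rule operative by sending the reader back to it: "For definition of evaluable patient for non-haematological and evaluable cycle/patient for haematological and biochemical toxicity". Neither document says what counts as assessed.

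**What period is counted.** Protocol 7.4: "The treatment period begins on the day of randomisation and continues until 30 days after the last study treatment administration". Protocol 7.3 says that all events after registration "will be taken into account in the analysis, whether the patient received the study treatment or not", and it allows at most one week between registration and first dose. SAP 5.1 says "Treatment Emergent Adverse Events (TEAE) will be considered for analysis of adverse events" and sets their window as "from first drug administration date up to last administration date + 30 days". The comparator for judging emergence is the worst grade in the two weeks before treatment. Protocol 11.5.4.2 also asks for treatment-emergent reporting but does not define it.

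**The concern.** A safety percentage needs one denominator, fixed before the data are seen. Here a programmer who follows SAP 7.4 and another who follows SAP 5.1 through 11.1 would produce different tables from the same data, and both would be following the plan. The term assessed is undefined, so someone must settle its meaning after the open-label data exist.

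The patients most likely to lack an assessment are those who leave early. Protocol Table 19 schedules toxicity review on day 1 of each cycle, and Table 20 schedules a final review within 30 days of stopping. After premature discontinuation, protocol 7.6 asks the investigator only to make every effort to obtain that final review. Early leavers are also the patients in whom early toxicity matters most, and their number may differ between a two-drug and a one-drug arm. SAP section 13 keeps a full description of safety after amendment 11, so the denominator of that description should not be in doubt.

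**Working it through.** The plan states no figure to reproduce, so the check compares the texts and then bounds the possible effect.

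**Step 1. Denominator for non-haematological adverse events**

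| Place | Condition |
|---|---|
| Protocol 7.6 and 11.3.4 | treated |
| SAP 7.4 and opening of 11 | treated |
| SAP Appendix 1, tables 12_2_1 and 12_2_2_1a to 1d | labelled Safety set, hence treated |
| SAP 5.1, via SAP 11.1 | treated **and** toxicity assessed |

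The last row conflicts with the other three. The SAP therefore contradicts itself as well as the protocol.

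**Step 2. Possible size.** Within an arm, let p be the event rate among all treated patients, m the share of treated patients not assessed, and q the event rate among those not assessed. The rate shown under SAP 5.1 is

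shown = (p − m·q) / (1 − m).

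The documents give none of p, m or q. Take p = 40% and m = 4% as assumptions.

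- No unassessed patient had the event (q = 0): 0.40 / 0.96 = 41.7%.
- All of them had it (q = 1): (0.40 − 0.04) / 0.96 = 37.5%.
- Same rate as the others (q = 0.40): (0.40 − 0.016) / 0.96 = 40.0%, no change.

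At m = 1% the range is (0.40 − 0.01) / 0.99 = 39.4% to 0.40 / 0.99 = 40.4%. If only one arm is affected at m = 4%, the between-arm difference moves by −2.5 to +1.7 points.

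The direction depends on the undefined word. If any recorded event counts as an assessment, the unassessed have no recorded events, q = 0, and the shown rate can only rise. If assessed means a scheduled toxicity review, a patient known only through a spontaneous or serious-event report could be left out, and the rate can fall.

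**Step 3. Window.** Protocol 7.4 starts at randomisation and SAP 5.1 at first dose. The gap is at most 7 days under protocol 7.3, so it lies inside the 14-day baseline period of SAP 5.1. An event that first arises in the gap therefore becomes the baseline comparator. It counts as treatment-emergent only if it later meets one of the SAP's worsening criteria. A never-treated patient has no first-dose date, so neither the window nor the baseline period is defined for that patient.

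**The case against.** The strongest reply is that nobody has been shown to be excluded. SAP section 11 names the all-treated population, every adverse-event table carries the Safety set label, and the 5.1 condition covers non-haematological toxicity only. Assessment is also broader than day-1 visits. There is the end-of-treatment review in Table 20, protocol 9.1.3 records events that are spontaneously reported or observed by others, and protocol 9.2 makes deaths within 30 days of the last dose serious events with an investigator causality assessment. A patient who dies in cycle 1 would normally have an investigator's report. All of this stands. It means that the number affected may be small or zero, but it does not remove the conflicting rule or the cross-reference that applies it.

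A reader might infer three stronger things, and the documents do not support them.

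- **That the adverse-event tables are labelled with a different population from the serious-event and death tables.** All carry the Safety set label in SAP Appendix 1.
- **That events before first dose, or in never-treated patients, appear in no table.** Pre-treatment events are tabulated on the ITT population (14_1_7). SAP 9.1.1 displays patient status and reason of death, and patient disposition is an ITT table. The 16.2.7 listings carry no Safety set restriction, and deaths from randomisation count in the ITT survival analysis. What is missing is narrower: the adverse-event, serious-event and death summaries are on the Safety set, and no summary isolates the interval from randomisation to first dose by arm.
- **That the first-dose window is a plain breach of the protocol.** Protocol 7.3 refers to the analysis without saying that it means the safety analysis, while protocol 11.3.4 limits safety to treated patients and 11.5.4.2 asks for treatment-emergent reporting. The protocol is itself inconsistent here.

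**Conclusion.** The point holds as a contradiction over the denominator. SAP 5.1, applied through 11.1, conflicts with protocol 7.6 and 11.3.4, with SAP 7.4 and 11, and with the label on the SAP's own tables. It is not established that any treated patient will be dropped. The texts permit it and do not say which rule prevails.

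The size is unknown. The range of 37.5% to 41.7% around 40% rests on an assumed 4% unassessed and on the two extreme event rates among them, so realistic effects at that share lie inside it. The consequence is an ambiguous set of adverse-event percentages, with an added post-randomisation selection in an open-label trial. Overall survival is untouched.

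The difference in treatment-period start is real but secondary. It affects at most one week per treated patient if protocol 7.3 is followed, and it calls for reconciliation of both documents rather than correction of the SAP alone.

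**What to change.** 1. In SAP 5.1, delete the second condition, the one requiring that toxicity was assessed, so that all adverse-event percentages use all treated patients as in SAP 7.4. Amend the SAP 11.1 cross-reference for non-haematological toxicity to point to 7.4. Leave the laboratory evaluability rules in 5.3 and 5.4 as they are.
2. Report by arm, for example as a line in table 12_2_1, the number of treated patients with no toxicity assessment after first dose, and define assessment for that count.
3. Reconcile the start of the treatment period across protocol 7.3, 7.4 and 11.5.4.2 and SAP 5.1. State where events between randomisation and first dose, and events in never-treated patients, are summarised. A row by randomised arm would do, but this is mainly a matter of presentation.

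The cost is one deleted clause, one amended cross-reference, one line of counts and a short clarification, all before database lock. No new data are needed, because protocol 7.3 already requires events after registration to be recorded.

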### **5.1.1. Adverse Events Of Special Interest**

Adverse Events Of Special Interest (AEOSI) will be presented to facilitate monitoring of the following MedDRA preferred terms or Highest Level Terms of special interest: Myelosuppression, Febrile Neutropenia, Infections with severe neutropenia: clinically relevant Infections (potential bacterial origin), Constipation, Ileus, Intestinal obstruction, Abdominal pain, Nausea, Vomiting, Stomatitis / Mucositis, Diarrhoea, Myocardial infarction/ Ischemia, Cardiac arrhythmias, Cardiac conduction disorders, Local injection/infusion site reactions, Extravasation, Peripheral sensory neuropathy, Peripheral motor neuropathy, Autonomic neuropathy, Asthenia/fatigue, Myalgia, Immediate hypersensitivity, SIADH, PRES, Hepatic dysfunction,.

AEOSI will be programmatically determined from a predefined list presented in appendix 3.

### **5.1.2. Serious Adverse Event**

A serious adverse event (SAE) includes, but is not necessarily restricted to, any event which:

- Results in death (whatever may be the cause),
- Is life-threatening,
- Results in persistent or significant disability/incapacity,
- Requires patient hospitalisation or prolongation of existing hospitalisation,

- Is a congenital anomaly or birth defect,
- Other events including cancer, overdosage, pregnancy and any additional adverse experience or abnormal laboratory values occurring during the study period defined by the protocol as serious or which the investigator considers significant enough or that suggests a significant hazard, contraindications, side effect or precaution will be handled as a serious adverse event.

Any overdosage meeting seriousness criteria should be reported as a SAE.

Any pregnancy occurring after patient exposure to study drug(s), should be reported on the SAE notification form.

All deaths occurring while the patient is on study including deaths due to disease progression and deaths within 30 days of last administration of study drug should be notified as SAE.

## 5.2. FEBRILE NEUTROPEMIA

According to CTCAE version 3.0, febrile neutropenia (FN) is defined as ANC <1.0 x 10^9/L and fever

- 38.5°C of unknown origin without clinically or microbiologically documented infection.

## 5.3. HAEMATOLOGICAL PARAMETERS

Haematological toxicity will be assessed by laboratory investigations of haemoglobin, WBC, ANC and platelets. Grades will be calculated according to CTCAE version 3.0.

A cycle will be evaluable for haematological toxicity analysis if the following criteria are fulfilled:

- At least one drop of any treatment,
- At least one blood cell count between Day 2 and Day 1 of next cycle or end of treatment period for the last administered cycle,
- At least one of the four haematological parameters analysed has been measured.

A patient is evaluable for haematological toxicity analysis if at least one cycle is evaluable.

## 5.4. BIOCHEMICAL PARAMETERS

Biochemical toxicity will be assessed by laboratory investigations of liver function tests (i.e. total bilirubin, alkaline phosphatase, AST, ALT), renal function tests (creatinine and calculated (Cockcroft-Gault formula) creatinine clearance) and glucose, total proteins, albumin, urea, sodium, potassium, calcium, bicarbonate, magnesium, chloride. Grades will be calculated according to the CTCAE version 3.0.

A cycle will be evaluable for biochemical toxicity analysis if the following criteria are fulfilled:

- At least one drop of any treatment has been administered,

- At least one biochemistry test between Day 2 and Day 1 of next cycle or end of treatment period for the last administered cycle,
- At least one of the sixteen biochemical parameters analysed has been measured.

A patient will be evaluable for biochemical toxicity analysis if at least one cycle is evaluable.

In addition, AST, ALT and bilirubin will be analysed according to the presence or not of liver lesions at baseline in order to assess the relationship between liver metastasis and worst grade during study.

The same analysis will be done for alkaline phosphatase according to the presence or not of liver/bone metastases.

## 6. OTHER PARAMETERS

[figure not shown]
### 6.1. CONCOMITANT MEDICATIONS

In the same way as the adverse events, concomitant medications will be coded using the specific international terminology WHO-Drug Dictionary version 2011, Q2.

### 6.2. QUALITY OF LIFE PARAMETERS

The European Organisation for Research and Treatment of Cancer (EORTC) score questionnaire (QLQ-C30) will be analysed as well as the QLQ-Head and Neck 35 EORTC module, to measure the health-related quality of life.

The QLQ-C30 and the QLQ-Head and Neck 35 EORTC module will be completed prior to randomization, every 6 weeks and at the end of treatment evaluation.

Health-related quality of life parameters will be the fifteen scales that can be derived from the 30 questions of the EORTC QLQ-C30 questionnaire:

- A global health-related quality of life scale,
- Five functional scales: physical, role, cognitive, emotional, social,
- Nine symptom scales: nausea and vomiting, pain, fatigue, dyspnoea, insomnia, appetite loss, constipation, diarrhoea, financial difficulties.

Of note, a higher value in functional scales will reflect a better level of function, but for "symptoms" scales a higher value will reveal a deterioration of the condition.

Each scale in the EORTC QLQ-C30 questionnaire will be scored (0 to 100) according to the EORTC recommendations in the EORTC QLQ-C30 Scoring Manual. The scoring method is summarized below. In this summary Qi refers to the  $i^{\text{th}}$  question on the EORTC QLQ-C30.

**Functional scales:**

- Physical functioning:  $(1 - ((Q1+Q2+Q3+Q4+Q5)/5 - 1)/3) * 100$
- Role functioning:  $(1 - ((Q6+Q7)/2-1)/3) * 100$
- Emotional functioning:  $(1 - ((Q21+Q22+Q23+Q24)/4-1)/3) * 100$
- Cognitive functioning:  $(1 - ((Q20+Q25)/2-1)/3) * 100$
- Social functioning:  $(1 - ((Q26+Q27)/2-1)/3) * 100$

